1.0 BACKGROUND

1.1 Structural heart disease causes calcium leak from the cardiac ryanodine receptor 2 channel (RyR2)

This is a randomized controlled trial that aims to study whether RyR2 inhibition with dantrolene reduces susceptibility to ventricular arrhythmias and improves hemodynamics in patients with structural heart disease. Figure 1 is the concept diagram of our proposed trial. The idea to be tested is that structural heart disease results in post-translational modifications to RyR2, which is the intracellular Ca channel, causing Ca to leave the sarcoplasmic reticulum and raising the concentration of intracellular Ca. This causes arrhythmias through delayed after depolarizations (DADs) that can trigger ventricular tachycardia (VT) and ventricular fibrillation (VF) and also are believed to contribute to changes in refractoriness and conduction that promote scar-related reentrant VT. Intracellular Ca overload also reduces cardiac Ca cycling which reduces cardiac contractility. Both conditions promote VT and VF which are the major causes of sudden cardiac death (SCD) in patients with structural heart disease.

1.2 Ventricular arrhythmias due to structural heart disease are a major cause of sudden cardiac death

An estimated 150,000 to 450,000 individuals suffer SCD per year in the U.S, and approximately 90% are estimated to have underlying coronary artery and/or structural heart disease (Figure 2).¹⁻⁴ Recent reports estimate VT or VF are detected as the initial rhythm in ~20% of SCD cases, however when there is a shorter time between collapse and initial rhythm detection this estimate increases to 75-80%.^{2,4} Along with improved strategies to identify at-risk individuals and increase the rate of successful resuscitation, new therapies are desperately needed to prevent the recurrence of VT/VF. Implantable cardioverter defibrillators (ICDs) can successfully terminate VT/VF, but do not prevent it. ICD shocks are associated with increased mortality, heart failure, post-traumatic stress disorder, and healthcare utilization.⁵⁻¹⁰ Furthermore, once VT occurs, it is likely to recur, thus therapies to prevent recurrent VT/VF (e.g. antiarrhythmic drugs [AADs]) are of great importance.¹¹⁻¹³

1.3 New pharmacologic therapies are needed to prevent VT/VF in structural heart disease.

In 2018 there are fewer AADs available for clinical use than 20 years ago.¹⁴ Discouraging the development of new agents are the problems associated with AADs that target ion channels on the cell surface. They possess a narrow therapeutic window with higher drug levels leading to pro-arrhythmia that is worse in structural heart disease. Currently available AADs target the cardiac sodium (Na) current, rapidly-activating potassium (K) current, beta-adrenergic stimulation, or multiple currents (e.g. amiodarone) and all have significant limitations. Class IC agents that predominantly block Na channels, (e.g. flecainide, propafenone) increase mortality in patients with structural heart disease and are relatively contraindicated in this population (CAST).¹⁵ K channel blockers prolong the QT interval, can cause polymorphic VT and have disappointing efficacy for VT. The risk of drug-induced torsades-de-pointes, a life-threatening VT, is

[figure not shown]

Figure 1: Concept Diagram for a Future Phase II Clinical Trial.

[figure not shown]

Figure 2: Structural heart disease due to CAD, cardiomyopathy, and valvular heart disease is a major cause of SCD. Image: Hayashi et al. (2015)

increased in structural heart disease due to down regulated K channels and abnormal calcium (Ca) homeostasis.^{16,17} Amiodarone is the most effective AAD for preventing recurrent VT/VF, but 10% of participants treated with amiodarone still have recurrent VT within one year and ~20% discontinue it due to potentially severe non-cardiac toxicities.¹² Furthermore, intolerance to amiodarone is more common at the doses used for refractory VT/VF.¹³

1.4 Mechanisms promoting monomorphic and polymorphic VT in structural heart disease.

In structural heart disease, monomorphic VT is most often due to reentry in regions of scar comprised of myocyte bundles and fibrosis. As [name] and others showed in early landmark studies, the arrhythmia substrate is often complex, such that numerous reentrant circuits are present giving rise to multiple different monomorphic VTs (pleomorphism) or polymorphic VTs.¹⁸⁻²³ In addition to reentry, automaticity and triggered activity are potentially important mechanisms contributing to VT in structural heart disease as they can provide the triggers necessary to initiate reentry, or in some cases may be the dominant mechanism.²⁴⁻²⁶ A major mechanism for triggered activity are DADs due to intracellular Ca overload. Abnormal Ca handling is well recognized in models of heart failure and hypertrophy. The diminished cell-to-cell coupling associated with fibrosis in areas of scar may also increase susceptibility to triggered automaticity resulting in an automatic VT or initiating a reentrant VT.²⁴⁻²⁶ Spontaneous Ca leak also inactivates Na channels which would be predicted to slow conduction velocity²⁷ and activates SK channels which shortens refractoriness²⁸⁻³², both of which may extend the excitable gap to promote scar-related reentry. Conditions that increase intracellular Ca are common in heart failure, especially β -adrenergic stimulation and increased heart rate. Relevant to our proposal is that dantrolene at clinically achievable doses has been found to reduce spontaneous Ca leak and DADs in ventricular cardiomyocytes isolated from failing human hearts without changing actional potential duration or reducing contractility.³³

A major knowledge gap we seek to address is the clinical potential of selectively targeting intracellular Ca to treat VT/VF in structural heart disease. Currently available AADs that reduce intracellular Ca are also potent Na channel blockers (e.g. flecainide, propafenone). Na channel blockade reduces conduction velocity and promotes scar-related reentry, thereby negating the benefit of RyR2 inhibition for reducing triggered activity in structural heart disease. Dantrolene inhibits RyR2-mediated Ca leak but does not block the Na channel.²⁷ By reducing spontaneous Ca leak, dantrolene may reduce Ca mediated Na channel inactivation thereby reversing slowed conduction in abnormal tissues. It also may reduce SK channel activation thereby reversing shortened refractoriness in abnormal tissues. Accordingly, an overarching goal of our work is to investigate the ability of RyR2 inhibition with dantrolene to speed conduction and prolong refractoriness in *diseased (low voltage) tissue*, and to assess whether it has a similar effect in *higher voltage tissue* that may have less fibrosis. Taken together, we seek to test the idea that selective RyR2 inhibition with dantrolene will reduce VT/VF in structural heart disease by reversing proarrhythmic changes in conduction and refractoriness that promote scar-related reentry.

1.5 Antiarrhythmic drugs and VT ablation: complementary approaches for refractory VT.

Presently ICDs are the major protection for prevention of SCD in patients with structural heart disease. Over 90,000 are implanted in the U.S. annually and within 2 years of implant up to 30% of patients will experience an ICD shock for an arrhythmia.³⁴ ICD shocks are associated with increased risk for heart failure and mortality despite the presence of the ICD and are associated with increased health care resource utilization.⁵⁻⁷ Shocks also reduce quality of life and cause post-traumatic stress disorder.⁸⁻¹⁰ Available

[figure not shown]

Figure 3: Ventricular arrhythmias induced using programmed stimulation following VT ablation. Image: Fujii, Stevenson and colleagues (2017).

AADs can reduce VT but have limited efficacy and significant toxicity¹², therefore ablation is an alternative therapy used to prevent VT.

The efficacy of ablation is also limited. In multicenter trials approximately ½ of patients experience a recurrence of VT during follow-up, although the VT frequency is reduced for many. VT ablation is superior to escalating AAD therapy in patients with a prior myocardial infarction who have VT during AAD therapy, however, many continue to require AADs following ablation.^{11,13,35} The acute effect of catheter ablation is typically assessed using programmed stimulation to induce VT at the end of the procedure. **Figure 3** presents the breakdown of ventricular arrhythmias that were acutely inducible following VT ablation by [name] and colleagues (N=165 patients).³⁶ These data support the design of a clinical trial proposing to study ventricular arrhythmias that remain inducible in patients following a VT ablation procedure. Monomorphic VT that lasted >30 seconds was induced in 38 patients, VF was induced in 9 patients, and non-sustained VT (NSVT) was induced in 34 patients. These arrhythmias are not ablated because an ablation target site could not be found or they do not match a VT that had been observed clinically (e.g. NSVT, VF, monomorphic VT that is much faster than spontaneously occurring VT), and therefore predict a lower risk of VT recurrence.³⁷ However, a major finding of this study was that inducible NSVT was a marker for VT recurrence. Similarly, inducible polymorphic VT/VF, and rapid monomorphic VTs are associated with an increased risk of spontaneous VT in other studies.^{37,38} Thus inducibility of these arrhythmias indicates the continued presence of an arrhythmia substrate which lends itself to the electrophysiologic assessment of therapy, particularly in paired, blinded assessments. In our proposal we selected a duration of 10 seconds as our definition for an inducible ventricular arrhythmia, as this has been used in other studies of drug assessment and reduces the likelihood of VT/VF requiring cardioversion.³⁹

1.6 The effect of dantrolene on muscle strength and respiratory mechanics.

A side effect of dantrolene is mild muscular weakness^{40,41}. The impact of dantrolene, specifically Ryanodex, on respiratory mechanics, however, is unclear. Dantrolene is typically given to patients with malignant hyperthermia who are intubated, who have been given neuromuscular blocking drugs, and who are under general anesthesia, since the triggers for malignant hyperthermia require general anesthesia or paralytic administration. We seek to measure the effect of the administration of dantrolene/Ryanodex on incidence of interventions to support respiration (bag/mask ventilation, CPAP, BiPAP, LMA placement, tracheal intubation) in the perioperative period. We will also compare additional markers of respiratory mechanics and strength (secondary endpoints) between groups including negative inspiratory force, dynamometer measured grip strength, accelerometer measured twitch strength and train-of-four, ventilation (respiratory rate, tidal volume, minute ventilation), markers of gas exchange (arterial pH, pCO₂, pO₂, base excess), and electrolytes.

2.0 RATIONALE AND SPECIFIC AIMS

Sudden cardiac death (SCD) accounts for up to 15-20% of all deaths per year in the U.S. and ventricular tachycardia (VT) and ventricular fibrillation (VF) from structural heart disease are major causes.^{2,42} To prevent these deaths, approximately 90,000 implantable cardioverter defibrillators (ICDs) are placed annually in the U.S. Up to 30% of these patients will have VT/VF terminated by the ICD within 2 years, often by a shock.^{34,43} Unfortunately, ICDs terminate VT/VF after it occurs, *but do not prevent it*. The occurrence of VT/VF is associated with increased risk of heart failure hospitalizations, and death, and once VT occurs, it is likely to recur.¹¹⁻¹³

For decades chronic therapy with antiarrhythmic drugs (AADs) has been the major option to prevent recurrence of VT/VF. Currently available AADs target the cardiac sodium (Na) current, rapidly-activating potassium (K) current, beta-adrenergic stimulation, or multiple currents (e.g. amiodarone). Through clinical trials (CAST¹⁵) and clinical experience, it was recognized that Na channel blockers increased mortality in patients with structural heart disease through scar-related VT. Similarly, QT-related proarrhythmia is a risk with K channel blockers. Amiodarone is the most effective AAD for preventing recurrent VT/VF, but 10% of participants treated still have recurrent VT within one year and ~20% discontinue it due to pulmonary toxicity,

thyroid toxicity and symptomatic bradycardia (OPTIC Trial).¹² Taken together, a major unmet need is the development of a new class of AADs to prevent VT/VF in structural heart disease.

Research by our group and others has focused on the role of diastolic calcium (Ca) leak via the RyR2 channel as a cause of delayed afterdepolarizations (DADs) and polymorphic VT in rare genetic disorders such as catecholaminergic polymorphic VT (CPVT).^{44,45} This led to the discovery that drugs which stabilize the RyR2 channel eliminate DADs and polymorphic VT in CPVT; this includes not only the experimental probe drug ent-verticilide but also clinically used agents such as flecainide and its derivatives and dantrolene, which is being studied here.^{46,47} The recognition that structural heart disease results in post-translational modification of RyR2 and diastolic Ca leak is consistent with the idea that Ca leak is also involved in generating VT/VF in more common diseases.⁴⁸⁻⁵¹ Accordingly, the **overarching hypothesis** to be tested is that RyR2 hyperactivity in patients with structural heart disease drives proarrhythmic changes in refractoriness and conduction, and decreases cardiac contractility, which promotes VT/VF (**Figure 1**).

Despite the success of flecainide to treat CPVT, it is relatively contraindicated in patients with structural heart disease because of its Na-channel inhibition. Dantrolene, a currently available drug that inhibits RyR2, but has no Na or K channel activity, will be used as a tool to study RyR2 modulation. Here, we propose a randomized controlled trial of dantrolene versus placebo in patients with structural heart disease referred for VT ablation to evaluate electrophysiologic, hemodynamic, and arrhythmia prevention endpoints. Dantrolene's inhibition of RyR1 will also be studied to define its effect on muscle and respiratory strength in this clinical population, which will be important if dantrolene is to be considered for repurposing as an antiarrhythmic drug. Accordingly, we propose the following Specific Aims:

Aim 1: To conduct a randomized, placebo-controlled trial of dantrolene to study the effect of RyR inhibition on cardiac electrophysiology, hemodynamics, arrhythmia inducibility, muscle strength, and respiratory mechanics in patients with structural heart disease referred for VT ablation.

Aim 2: To explore the pharmacokinetic/pharmacodynamic relationship of I.V. dantrolene and its short-term effect on cardiac electrophysiology, hemodynamics, and muscle and respiratory strength.

3.0 ANIMAL STUDIES AND PREVIOUS HUMAN STUDIES

3.1 Experimental evidence: RyR2 inhibitors treat VT/VF and improve hemodynamics

Experimental evidence from animal models of VF and scar-related VT demonstrates the efficacy of RyR2 inhibition with dantrolene to treat and prevent VT/VF.⁵² In a swine model, treatment with I.V. dantrolene administered during VF decreased the number of shocks required for successful defibrillation, the time to return of spontaneous circulation (defined as systolic blood pressure >60 mmHg), and the number of episodes of refibrillation.⁵² Dantrolene (2 mg/kg) was administered during CPR 3 minutes prior to attempted defibrillation, suggesting the myocardial uptake and pharmacodynamic effect of dantrolene on cardiac electrophysiology is rapid. Refibrillation was initiated by a premature ventricular complex (PVC) in 96% of cases and the proportion of animals refibrillating was 71% (5/7) in the control group compared to 27% (3/11) in the dantrolene group, supporting the ability of dantrolene to reduce spontaneous ventricular ectopy.

In preliminary data generated by [name] (unpublished), mouse infarct models were generated by coronary ligation which resulted in a chronic transmural infarct involving ~50% of the LV. A wildtype model and a transgenic heterozygous calsequestrin-2 (*Casq2*^{+/−}) knockout model were used. Heterozygous

Casq2 mice have hyperactive RyR2 Ca release, but do not exhibit catecholaminergic polymorphic VT (CPVT) as seen in homozygous *Casq2* mice. 3-4 weeks after coronary ligation, mice underwent programmed stimulation using transesophageal pacing. Monomorphic VT was inducible. Treatment with dantrolene (Ryanodex) or ent-verticilide (an investigational RyR2 specific inhibitor) significantly reduced inducible VT and ventricular ectopy (premature ventricular complexes) compared to vehicle (placebo) (**Figure 4**). These data support the idea that RyR2 inhibition with dantrolene reduces scar-related monomorphic VT in experimental models and supports our plans to advance this research into clinical investigation.

[figure not shown]

Figure 4: RyR2 inhibition with dantrolene (Ryanodex) and ent-verticilide reduces inducible VT and ventricular ectopy compared to vehicle (placebo) in a *Casq2*^{+/−} chronic infarct mouse model (unpublished data courtesy of [name]/PhD).

3.2 Single dose and chronic oral exposure to dantrolene in humans

In an unpublished Phase 1 study conducted to support the FDA application for Ryanodex (approved in 2014), 30 healthy volunteers were given a single I.V. dose of Ryanodex (1.0, 1.75, 2.0, 2.25, and 2.5 mg/kg). Adverse reactions were dose dependent and the most common were flushing (27% of subjects) and somnolence (13%). All adverse events were classified as mild/moderate and spontaneously resolved without sequelae. There were no severe or serious adverse events and no dose limiting toxicity. There were no significant changes from baseline in vital signs or ECG assessments. Recently, the experience of patients prescribed chronic oral dantrolene for the treatment of muscle spasticity was reported.⁵³ In 20 patients with a mean of 10.9 years of follow-up on oral dantrolene there were no major cardiac events, no QTc or QRS prolongation, and no change in cardiac function on serial echocardiograms.

3.3 A pilot study to demonstrate the feasibility of I.V. dantrolene to study the effects of RyR inhibition in patients with structural heart disease undergoing VT ablation

4.0 INCLUSION/EXCLUSION CRITERIA (TABLE 1)

Inclusion
≥18 years of age
Able to give written, informed consent
Referred for catheter-based VT ablation or PVC ablation
Structural heart disease (LVEF < 50%, history of prior myocardial infarction, cardiac sarcoid or valvular heart disease)
Permanent pacemaker or implantable cardioverter defibrillator
Exclusion
Mechanical ventricular support (e.g. LVAD, ECMO)
NYHA class IV heart failure
LVEF <20%
Severe renal insufficiency (GFR<30 mL/min)
Morbid obesity (BMI≥ 40 kg/m ²)
Chronic liver disease (Child Pugh class A-C)
Current use of calcium channel blockers
Neuromuscular disorder (e.g. muscular dystrophy)
Chronic obstructive pulmonary disease or restrictive lung disease requiring oxygen therapy or history of intubation
Pregnant or nursing
History of dysphagia

5.0 ENROLLMENT AND RANDOMIZATION

Table 1. Eligibility Criteria

Recruitment and informed consent: Eligible subjects will be identified by either: 1) Arrhythmia Clinic nurses or physicians will contact a member of the study team if they are scheduling an eligible subject for VT ablation or PVC ablation, or 2) the study coordinator will review the EP Lab schedule for VT and PVC ablation cases and screen their medical record for eligibility. The study coordinator will then request the clinical staff to obtain permission from the patient to contact them about research. If the patient agrees, a member of the study team will approach the patient in person in Arrhythmia Clinic, Vanderbilt University Hospital, or by phone prior to ablation. Information describing the study, why the research is being done and what will be learned will be provided. The risks as described in this protocol will be delineated. The benefits will be described as general scientific knowledge, along with potential treatment advances. No direct immediate benefit to the subjects is anticipated. The patient will be given either a hard or electronic copy of the informed consent document. At least 24 hours will be given for the patient to consider participation after which the study coordinator will recontact the patient. If the patient desires to participate, informed consent will be documented with the subject's signature using the IRB-approved consent form for this protocol. This will occur in Arrhythmia Clinic or Vanderbilt University Hospital. If participation is being discussed with the patient by phone, a tentative agreement to participate will be obtained and the study coordinator will meet the patient on the morning of the procedure at Vanderbilt University Hospital to sign the informed consent document.

Randomization: 84 participants will be randomly assigned in a 2:1 ratio to treatment (dantrolene) or control (placebo). A computer-generated randomization list will be prepared by the study statistician using the stratified permuted block randomization, where block size varies randomly from 4 or 6 to ensure overall balance across treatment arms. Randomization will be stratified by 1) amiodarone use within the past 21 days defined as chronic oral use or >5 grams cumulative dose including ongoing use and 2) planned PVC vs. VT ablation. The study statistician will generate the allocation schedule but will remain blinded to the treatment assignment.

Dropouts and replacement: To ensure adequate statistical power, we will account for up to a 20% rate of patient withdrawal from the study prior to randomization (for reasons such as non-study related procedural complications, hemodynamic instability, prolonged case duration), therefore up to 105 participants may need to be enrolled for 84 participants to complete the study.

Study Drugs: The investigational compound is dantrolene sodium (RYANODEX, Eagle Pharmaceuticals Inc, Woodcliff Lake, NJ). Ryanodex is supplied in a single dose vial by the manufacturer and it is reconstituted with 5 mL of sterile water prior to use. Each vial contains 250 mg of Ryanodex. Based on results from the pilot study, Ryanodex will be administered as an I.V. push over 3 minutes at a dose of 1 mg/kg. Ryanodex was tested in a Phase I study and safely tolerated in doses ranging from 1 mg/kg to 2.5 mg/kg. It is approved for use in adults with malignant hyperthermia at a recommended dose of 2.5 mg/kg. The calculated dose is based on measured body weight with a maximum dose of 250 mg used in our trial.

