Conduction Time: is a continuous measurement. To most accurately measure conduction time, it is the mean value of multiple measurements along the horizontal aspect of the conduction curve (**Figure 7**). Conduction time is analyzed separately for the low voltage and higher voltage areas. Multivariable linear regression models will be built. Simple linear regression models will be used to test whether treatment with dantrolene is associated with a statistically significant decrease in mean post-drug conduction time when adjusted for mean pre-drug conduction time. Multivariable linear regression models will include additional adjustment for age, sex, mean bipolar voltage, amiodarone exposure (yes/no), change in beta-agonist exposure, and time from start of drug to post-drug EPS. Mean bipolar voltage will be the mean of the peak electrogram measured on the recording electrode for each of the extrastimuli.

Effective Refractory Period: is a continuous measurement. The ERP is measured at within the low voltage area and higher voltage areas at a drive train of 600 ms. It is measured pre-study drug and post-study drug. Multivariable linear regression models will be built. Separate models will be built for the low and higher voltage areas. Simple linear regression will test whether treatment with dantrolene is associated with a statistically significant increase in mean post-drug ERP when adjusted for mean pre-drug ERP. Multivariable analysis will be conducted using the same methods as described for conduction time.

Secondary Analyses Aim 1: activation time and conduction restitution are additional metrics for conduction. They are analyzed with the same statistical approach as described for conduction time.

Sample Size and Power Aim 1: The primary endpoints are conduction time and ERP. Pre- and post-drug difference in average conduction time and ERP will be compared between the dantrolene and the placebo group. We expect the conduction time to decrease and ERP to increase substantially after drug in the treatment arm, while no change is expected in the placebo arm. With 56 patients treated with dantrolene and 28 placebos, there will be 80% power to detect a $0.6 \times SD$ difference in the average conduction time and the average ERP change between the two study arms.

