Hemodynamic Endpoints: The primary hypothesis in Aim 2 tests whether RyR2 inhibition increases cardiac output and decreases PA diastolic pressure in patients with structural heart disease. The primary endpoints are cardiac index and mean PA diastolic pressure. Secondary endpoints are RA and PA pressures, RV stroke volume index, PA pulsatility index, and systemic and pulmonary vascular resistances.

Primary Analysis (Aim 2): Our primary analyses use multivariable linear regression to test whether our primary determinant (dantrolene vs. placebo) is associated with: 1) post-drug mean cardiac index and 2) post-drug mean PA diastolic pressure. Adjustment is made for pre-study drug measurements. Additional adjustment in the multivariable model includes: age, sex, LV ejection fraction (continuous), change in beta-agonist exposure, ventricular arrhythmia induced (yes/no), and time from start of study drug to post-drug hemodynamic measurements. Mixed-effect models with linear regression will be built for the repeated measurements to account for the correlation structure in the data, where patient ID will be treated as a random effect. Fixed effect factors include treatment arm, measurement time (1,2,3, etc.), and all covariates. The cardiac index and PA diastolic pressure adjusted for pre-drug measurements is presented for both treatment arms, together with corresponding 95% confidence intervals (CIs) and p-values are graphically interpreted using boxplots, partial effect plots, residual plots, etc.

Secondary Analysis (Aim 2): Secondary endpoints are RA and PA pressures, PA pulsatility index, and systemic and pulmonary vascular resistances. They are analyzed with the same statistical approach as described for output and PA diastolic pressure.

Sample Size and Power Aim 2: The pre- and post-drug difference in average cardiac index and PA diastolic pressure will be compared between the dantrolene and the placebo group. We expect the cardiac output to increase and PA diastolic pressure to decrease substantially after drug in the treatment arm, while no change is expected in the placebo arm. However, to allow for unexpected effects (e.g. negative inotropy), two-sided tests will be performed. With 56 patients treated with dantrolene and 28 with placebo, the study will provide 80% power to detect a $0.6 \times SD$ difference in the average cardiac index and the average PA diastolic pressure change

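### Permuted blocks of 4 cannot hold a 2:1 allocation, so the randomisation rule as written does not produce the planned 56:28 split

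*Combined protocol and SAP*

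**What the plan says.** The Randomization paragraph of Section 5.0 sets the ratio: "84 participants will be randomly assigned in a 2:1 ratio to treatment (dantrolene) or control (placebo". It then gives the method: "A computer-generated randomization list will be prepared by the study statistician using the stratified permuted block randomization", with the block rule "where block size varies randomly from 4 or 6 to ensure overall balance across treatment arms". There are two stratification factors. The first is "Randomization will be stratified by 1) amiodarone use within the past 21 days" and the second is "planned PVC vs. VT ablation", which makes four strata.

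Section 10.0 relies on the ratio. The Aim 1 sample-size paragraph begins "With 56 patients treated with dantrolene and 28 placebos", and the Aim 2 paragraph has "With 56 patients treated with dantrolene and 28 with placebo, the study will provide 80% power". The Aim 3 paragraph, which says that the trial was sized on the ordinal inducibility endpoint, gives the ratio as 1:2 placebo to treatment. No section says how a block of 4 is split between the arms.

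**The concern.** In permuted-block randomisation each complete block reproduces the target ratio exactly, and that is how balance is maintained. At 2:1 this requires a block size divisible by 3. Six qualifies and four does not. The ratio and the block sizes in the same paragraph therefore cannot both be followed.

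Three things are at stake:

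- **The realised split.** It depends on a choice that is not written down and on how many blocks of each size are drawn.
- **The allocation probability.** It would differ between blocks of 4 and blocks of 6, so the realised ratio could also differ between strata, which is what stratified blocking is meant to prevent.
- **Reproducibility.** A list built by anyone following this text will not match the described method in at least one respect, and the published description of the randomisation would be wrong.

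**Working it through.** **Inputs.** From Section 5.0: 84 randomised, ratio 2:1, block sizes 4 and 6, four strata. From Section 10.0: 56:28, a difference of 0.6 SD, and a two-sided 5% level (stated for Aim 2; applied here to the 0.6 SD comparison generally). My assumption: sizes 4 and 6 are equally likely, since no probabilities are given.

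**The plan's split.** 84 × 2/3 = 56 and 84 × 1/3 = 28. The stated 56:28 is reproduced.

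**Block check.** A block of size b needs 2b/3 dantrolene slots.

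- b = 6: 4, so 4:2.
- b = 4: 2.67, not a whole number. The nearest feasible splits are 3:1 and 2:2.

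**Long-run ratio.** Let w be the share of blocks that have size 4. The share on dantrolene is:

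- 4-blocks as 3:1: (3w + 4(1 − w)) / (4w + 6(1 − w)) = (4 − w)/(6 − 2w)
- 4-blocks as 2:2: (2w + 4(1 − w)) / (4w + 6(1 − w)) = (4 − 2w)/(6 − 2w)

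At w = 1/2 these are 7/10 (58.8:25.2 of 84) and 6/10 (50.4:33.6). Both formulas equal 2/3 only at w = 0, that is, when no blocks of 4 are used. At the other extreme, w = 1, they give 63:21 and 42:42.

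**Power at 0.6 SD.** Power ≈ Φ(0.6/√(1/n₁ + 1/n₂) − 1.96).

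| Split | 0.6/√(1/n₁ + 1/n₂) | Power |
|---|---|---|
| 56:28 (planned) | 2.592 | 73.6% |
| 59:25 (4-blocks 3:1) | 2.514 | 71.0% |
| 50:34 (4-blocks 2:2) | 2.699 | 77.0% |
| 63:21 (3:1, only 4-blocks) | 2.381 | 66.3% |
| 42:42 (2:2, only 4-blocks) | 2.750 | 78.5% |

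The 73.6% at the exact 56:28 split is below the stated 80%. That gap has nothing to do with block size. The calculation makes no allowance for adjustment for the pre-drug value.

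**Ordinal endpoint.** I took an odds ratio of 0.3 with 50% of placebo patients non-inducible and five further categories at 10% each, the number that makes the probabilities sum to 1. Approximate power, by a proportional-odds formula with two ways of averaging the category probabilities, is 69% to 72% at 56:28, 66% to 70% at 59:25 and 74% to 76% at 50:34. The shifts are again a few points in either direction.

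**Simulated lists.** Four strata, 84 participants, last blocks cut off where recruitment ends. Results were nearly the same for equal and unequal stratum sizes.

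| Rule | Mean on dantrolene | 95% range | Exactly 56 |
|---|---|---|---|
| 4 (2:2) and 6 | 50.2 | 46 to 54 | about 0.1% |
| 4 (3:1) and 6 | 58.9 | 57 to 61 | about 2% |
| 3 and 6 | 56.0 | 54 to 58 | about 40% |
| 6 and 9 | 56.0 | 54 to 58 | about 35% |

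Under either fixed filling of the blocks of 4, the planned 56 lies outside the 95% range.

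**The case against.** The best defence is that 2:1 can be kept on average with blocks of 4. If each such block is drawn as 3:1 with probability 2/3 and as 2:2 with probability 1/3, the expected number on dantrolene is 3 × 2/3 + 2 × 1/3 = 8/3, which is two thirds of 4. Simulated lists then average 56:28, with a 95% range of 53 to 59. This is valid arithmetic, but the protocol describes no such rule, and even under it no single block of 4 is 2:1. It shows that 2:1 is unattainable by the rule as written, not by every conceivable rule that uses blocks of 4.

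A second objection is that no stratified blocked list guarantees exactly 56:28, because the last block in each stratum may be incomplete. That is correct. The difference is one of kind: with multiples of 3 the scatter is small and centred on 56, whereas fixed 4-blocks move the centre.

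A third objection is that little is lost. Assignment stays random, power moves by a few points, and the 2:2 reading raises it. This also stands, and it rules out any claim of bias or of a seriously underpowered trial. It does not make the instruction executable.

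Finally, the actual list is not in the documents. It may already use suitable block sizes, in which case only the text is wrong.

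**Conclusion.** The concern holds. Section 5.0 contradicts itself: a 2:1 ratio cannot be delivered by blocks of 4, and the missing rule for filling them is given nowhere. With fixed compositions and equal use of the two sizes, the expected split is about 59:25 or 50:34 instead of 56:28. The departure is three more or six fewer participants on dantrolene, and about 3 percentage points of power either way at 0.6 SD. The sizes depend on the assumed equal mix and the unadjusted normal approximation. The contradiction itself depends on neither.

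Correction is necessary because the allocation rule cannot be carried out as written and is the basis for the ratio used in the Aim 1, Aim 2 and ordinal Aim 3 power statements. The size of the power change would not by itself require it.

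**What to change.** Replace the block sizes in Section 5.0 with multiples of 3, varied at random within each of the four amiodarone-by-planned-ablation strata. Sizes 6 and 9 are the better choice. Sizes 3 and 6 keep the total slightly closer to 56 (about 99% of simulated lists within 2, against about 97% for 6 and 9). But in a block of 3 the remaining assignments are known once the single placebo slot is recognised.

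Before amending, have someone independent of the blinded team inspect any list already generated. If it was built in multiples of 3, only the text needs correcting. If it contains blocks of 4, replace the unused part, and record how those blocks were filled and what ratio resulted. Also confirm that the list is at 2:1 at all. Sizes 4 and 6 both suit 1:1 allocation, so the sentence may have been carried over from a 1:1 design; that is conjecture, but easy to check.

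The cost is a one-line amendment and regeneration of unused assignments. No endpoint, visit or sample size changes.
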